PASS INFORMATION

Title	Multicenter prospective open-label non-interventional uncontrolled Post-Authorisation Safety Study (PASS) to evaluate the safety profile of Polyoxidonium in daily practice
Protocol identification No:	PETRO/2015-01
Protocol version identifier	Final version 1.1
Date of last version of protocol	3 February 2016
EU PAS register number	to be specified
Active substance	Azoximer bromide Pharmacotherapeutic group: other cytokines and immune modulators ATC code: L03AX
Medicinal product	POLYOXIDONIUM [®] 6 mg lyophilisate for solution for injection
Product reference	59/0220/02-S (national)
Procedure number	-
Marketing authorisation holder	MEDIGROUP s.r.o.
Sponsor:	NPO PETROVAXPHARM [name]
Joint PASS	No
Research question and objectives	
This PASS aims to collect data on the safety of Polyoxidonium in patients, for whom Polyoxidonium is prescribed in routine practice in accordance with the terms of the marketing authorisation (MA).
 
The primary objective is:
 
- to assess the frequency of adverse drug reactions- to estimate the proportion of subjects, who develop signs and symptoms of adverse renal effects associated with the use of Polyoxidonium. 
Secondary objective is to evaluate the clinical benefit of Polyoxidonium.

Country of study	Slovak Republic
Author	[name], MSc, Medical Expert (CRO Biomapas)

MARKETING AUTHORISATION HOLDER

Marketing authorisation holder(s)	MEDIGROUP s.r.o. [name] [contact] [contact] E-mail: [contact]
MAH contact person	[name], QPPV [contact] E-mail: [contact]

The information contained in this document is confidential. By accepting this document you agree that the information contained herein will not be disclosed or reproduced without written authorization from NPO PETROVAXPHARM.

Throughout this documents, symbols indicating proprietary names (®, TM) may not be displayed. Hence, the appearance of product names without these symbols does not imply that these names are not protected.

POLYOXIDONIUM

PASS PROTOCOL
PETRO/2015-01
Final version 1.1. 3 February 2016

PASS PROTOCOL APPROVAL FORM

**MULTICENTER PROSPECTIVE OPEN-LABEL NON-INTERVENTIONAL
UNCONTROLLED POST-AUTHORISATION SAFETY STUDY (PASS) TO
EVALUATE THE SAFETY PROFILE OF POLYOXIDONIUM IN DAILY PRACTICE**

Protocol (study) identification No: PETRO/2015-01

2. LIST OF ABBREVIATIONS

ADR	Adverse Drug Reaction
AE	Adverse Event
CRO	Contract Research Organisation
DM	Data Management
EC	Ethics Committee
eCRF	electronic Case Report Form
ECG	electrocardiogram
ENCePP	European Network of Centers for Pharmacoepidemiology and Pharmacovigilance
GPP	Good Pharmacoepidemiology Guidelines
ICD-10	International Classification of Disease, 10th rev.
ICD-9	International Classification of Disease, 9th rev.
ICF	informed consent form
MAH	Marketing Authorization Holder
MedDRA	Medical Dictionary for Regulatory Activities
PASS	Post authorization safety study
QPPV	qualified person in pharmacovigilance
RA	Regulatory Authorities
RMP	Risk Management Plan
SAE	Serious Adverse Event
SAP	Statistical Analysis Plan
SmPC	Summary of Product Characteristics
SOPs	Standard Operating Procedures
WBC	white blood cells

4. ABSTRACT

Title

Multicenter prospective open-label non-interventional uncontrolled Post-Authorisation Safety Study (PASS) to evaluate the safety profile of Polyoxidonium in daily practice.

Protocol version: final version 1.1 3 February 2016.

Protocol author: [name], MSc, Medical Expert at CRO Biomapas.

Rationale and background

Data from Polyoxidonium acute and sub-acute toxicity studies in rodents and chronic toxicity in dogs showed the potential risk of renal toxicity.

Although no adverse effects on renal system were reported in Polyoxidonium clinical trials development programme and during routine post-authorisation pharmacovigilance activities, the potential renal effect cannot be ruled out.

The safety signal known from pre-clinical phase of development needs to be further investigated.

Research question and objectives

This PASS aims to collect data on the safety of Polyoxidonium in patients, for whom Polyoxidonium is prescribed in routine practice in accordance with the terms of the marketing authorisation (MA).

Primary objectives:

- to assess the frequency of adverse drug reactions;
- to estimate the proportion of subjects, who will develop signs or symptoms of adverse renal effects associated with the use of Polyoxidonium.

Secondary objective is to evaluate the clinical benefit of Polyoxidonium by evaluating the following variables:

- overall clinical improvement as assessed by investigators and subjects;
- mean duration of primary treatment of disease;
- mean number of days with fever $>38^{\circ}\text{C}$ and (or) disease symptoms;
- change in total and differential white blood cells (WBC) count (blood and urine) from baseline to the end of treatment (if data are available).

Study design: local, multicenter, prospective, open-label, non-interventional, uncontrolled study.

The decision to prescribe Polyoxidonium will be independent of the decision to enrol the subject into the study. Each subject will be observed for the duration of one cycle of Polyoxidonium treatment. In accordance with the SmPC, the treatment course consists of 5-10 injections depending on the disease. Thus, study duration for individual subject will take 7-23 days. There will be 5-10 study visits coinciding with routine visits to receive Polyoxidonium injections at the health care centre.

Actual assessments undertaken at each visit will be determined by clinical practice (see Study flow chart in Table 1). Subjects will not be administered any investigational medicinal products

and/or medical procedures neither undergo any laboratory evaluations, diagnostic or monitoring procedures specifically for the purposes of this study.

Population: The study will be conducted by immunologists or allergologists in primary or secondary care setting in Slovak Republic.

To be eligible for participation in this study, the patient must:

- a) be male or female at least 18 years of age.
- b) receive Polyoxidonium prescription in accordance to the SmPC currently approved in Slovakia, i.e., for the treatment of any of the following diseases or conditions accompanied by secondary immunodeficiency:
 - chronic recurrent bacterial infection;
 - chronic recurrent viral infection;
 - acute bacterial infection;
 - acute viral infection;
 - allergic disease (pollinosis, bronchial asthma, atopic dermatitis).
- c) be informed about the study and provide written consent to participate.

The patient can't take part in the study if:

- (a) Polyoxidonium is contraindicated as per SmPC;
- (b) investigator deems necessary to prescribe more than 10 injections of Polyoxidonium per a single treatment course for the given patient.
- (c) patient has any clinically significant underlying medical illness, condition or disorder that, in the judgment of the investigator, could interfere with the conduct of the study.
- (d) patient is currently enrolled in any other investigational study or has participated in a interventional study within 4 weeks before enrolment.

Variables

Event of interest is signs or symptoms of adverse renal effects. In case of suspected adverse renal effect investigator will be encouraged to perform diagnostic workup and collect as much data as possible to confirm or reject the diagnosis of renal impairment. These data for each subject for whom adverse renal effect is suspected will be reviewed and adjudicated by an independent assessor. This final adjudicated conclusion will be qualified as event of interest (a case of adverse renal effect) or suspicion about renal toxicity will be rejected.

Safety variables include:

- proportion of subjects with adverse renal effect (as defined in Section 9.3.1)
- proportion of subjects, who experienced any AE;
- proportion of subjects with ADRs;
- proportion of subjects experiencing serious adverse events (SAEs);
- proportion of subjects with serious ADRs;
- severity of AEs;
- number of subjects who discontinued the study and the reasons for drop-outs;
- global assessment of tolerability by investigators: very good (no intolerance reactions), good (occasional intolerance reactions), moderate (frequent intolerance reactions), poor (intolerance reactions after every use);
- global assessment of tolerability by subjects: very good, good, moderate and poor

Clinical benefit assessment includes the following variables:

- global assessment of improvement by subjects score (0 to 4 scale: 0=much worse; 1= somewhat worse; 2=same; 3=somewhat improved; 4 = greatly improved)
- global assessment of improvement by investigators score (0 to 5 scale: 0 = worse; 1 = no appreciable improvement; 2 = slight improvement; 3 = moderate improvement; 4 = marked improvement; 5 = complete resolution)
- mean duration of primary treatment of disease (i.e., days with antibiotic use in case of infection or antiallergic medication in case of allergies),
- days with fever >38°C/days with symptoms,
- total and differential WBC count in blood and urine (if data are available).

Data sources

Data collection will be based on the review of medical records and routine examination of subjects. Regular medical records at study sites will serve as data sources.

Study size

Approximately 500 adult subjects

Data analysis

Descriptive and comparative statistical methods will be used.

A stratified analysis of main event of interest (i.e., adverse renal effect) will be performed by prior renal impairment and by use of concomitant nephrotoxic medicines to control confounders. Logistic regression will be employed to determine factors as possible predictors of adverse renal effect.

Stratified analysis by indication will be performed to investigate safety profile and clinical benefit in different subgroups of subjects.

Milestones

First eligible subject is planned to enrol on May 2016. Last subject last visit is expected to occur in November 2016.

5. AMENDMENTS AND UPDATES

None.

6. MILESTONES

Milestone	Planned date
Start of data collection	May 2016
End of data collection	December 2016
Registration in the EU PAS register	February 2016
Final report of study results	March 2017

7. RATIONALE AND BACKGROUND

7.1. Background

Immunodeficiency may occur both in the young and in the elderly, with immune responses beginning to decline at around 50 years of age due to gradual deterioration of the immune system. In developed countries, obesity, alcoholism, and drug use are common causes of poor immune function, whereas malnutrition is the most common cause of immunodeficiency in developing countries. Additionally, the loss of the thymus at an early age, chronic granulomatous disease, AIDS, some types of cancer (or cancer therapies) or other medical conditions can cause immunodeficiency.

Azoximer bromide, the active substance of Polyoxidonium, is a copolymer of N-oxidised 1,4-ethylenepiperazine and (N-carboxyethyl)-1,4-ethylenepiperazine bromide. Polyoxidonium influences certain immunogenic effects through the following mechanisms of actions:

- activates three major subpopulations of phagocytes: mobile tissue macrophages, circulating cells in blood, and fixed phagocytes in the reticulo-endothelial tissue. In particular, a migration of macrophages, as well their ability to phagocytize and to digest pathogenic bacteria, are activated. Furthermore, the adhesive activity of polymorphonuclear leukocytes increase, as well as their ability to produce reactive oxygen species upon contact with the opsonized fragments of microorganisms.
- Improves the interaction between T- and B-lymphocytes in the processes of antibody formation in response to foreign antigens. Polyoxidonium is distinguished from other mitogens, such as bacterial lipopolysaccharide and plant lectins, by its attributes of not inducing a polyclonal transformation of B-cell lymphocytes into cells that secrete immunoglobulins and not causing multiple cycles of cell division of B- and T-lymphocytes in the absence of antigenic stimulus.
- Increase the intensity of the antibody formation in response to antigens, in particular cellular corpuscular antigens (heterologous erythrocytes) after administration of the drug. Irrespective of the genetically determined ability of the organism to form the immune

response to any given antigen, the administration of Polyoxidonium stimulates antibody responses in both high- and low-reactive genotypes.

By stimulating the immune responses, Polyoxidonium does not alter the natural mechanisms of inhibition. In particular, the formation of T-suppressor cells, as well as the functioning of the already formed T-suppressor cells, stay unaffected after immunostimulatory dose of Polyoxidonium. By stimulating the immune system, Polyoxidonium does not deplete the reserve capacity of hematopoietic system. The quantity of hematopoietic stem cells in the bone marrow tissue, as well as the ability of these cells to proliferate and differentiate into specialized directions of development (erythroid, granulocytic, monocytic or megakaryocytic), had been shown to stay fully preserved after immunostimulatory dose of Polyoxidonium. Therefore, a single or multiple dose of Polyoxidonium intended to stimulate the immune responses in healthy organism with normal immune status does not affect the peripheral blood cells.

7.2. Rationale of this study

Polyoxidonium has been marketed for almost 20 years (it was first launched in 1996 in Russia). In Slovak Republic, Polyoxidonium is available since 2002. It is estimated that during the period from 1996 to 2013 (inclusive) the total number of approximately 1,025,000 patients worldwide have used Polyoxidonium. No adverse effects specifically affecting any of organ systems have been reported in clinical development programme and during routine post-authorisation pharmacovigilance activities.

Data from Polyoxidonium acute and sub-acute toxicity studies in rodents and chronic toxicity studies in dogs showed the potential risk of nephrotoxicity, which occurred at doses well above the therapeutically relevant dose range. Nephrotoxic effect was observed in dogs after 40 daily injections of Polyoxidonium at doses 10 times exceeding the maximum recommended human dose and in rats after 15 daily injections at doses as high as 100 times the maximum recommended human dose. Besides, Polyoxidonium is predominantly excreted by kidneys.

During chronic toxicity research in dogs, the administration of 10 times the therapeutic dose of Polyoxidonium intramuscularly daily for a period of three months did not affect the ECGs, peripheral blood cells, and protein, carbohydrate and lipid metabolism. At the same time, already after two months of administration of Polyoxidonium a moderate increase in transaminase activity, as well as an increase in the alkaline phosphatase, bilirubin, creatinine, and urea concentrations in the blood serum had been observed, all of which became more pronounced after three months of administration. Histopathological examination of internal organs, performed at the end of experiment, had shown that long-term daily administration of Polyoxidonium at 10 times the therapeutic dose (1 mg/kg) led to the development of glomerulitis, changes in renal tubular apparatus, and degeneration of protein and fatty hepatocytes in dogs. Based on the results obtained from the research of systemic toxicity of the drug Polyoxidonium (acute and sub-acute toxicity in rodents and chronic toxicity in dogs), it was possible to conclude that the kidneys are the only target organ of Polyoxidonium. Meanwhile, biochemical and histological studies in rats had shown no damaging effects on the kidneys after 3-month administration of the drug Polyoxidonium 100 times the maximum recommended dose (25 mg/kg) with intervals between injections. The intervals between injections significantly reduce the nephrotoxic effects of the drug Polyoxidonium, moreover there was no nephrotoxic effect was not observed when the drug was temporary withdrawn for up to 7 days.

Although no adverse effects on renal system have been reported in Polyoxidonium clinical development programme and during routine post-authorisation pharmacovigilance activities, the potential adverse renal effects need to be further investigated.

A non-interventional post-authorisation safety study will be undertaken to systematically collect safety information under real-life conditions in patients receiving Polyoxidonium therapy. The special focus of this PASS will be on signs or symptoms of potential adverse renal effects.

8. RESEARCH QUESTION AND OBJECTIVES

This PASS aims to collect data on the safety of Polyoxidonium in patients, for whom Polyoxidonium is prescribed in routine practice in accordance with the terms of the marketing authorisation (MA). This study is a part of a Risk Management Plan (RMP).

The primary objective is:

- (a) to assess the frequency of adverse drug reactions
- (b) to estimate the proportion of subjects, who develop signs and symptoms of adverse renal effects associated with the use of Polyoxidonium.

Secondary objective is to evaluate the clinical benefit of Polyoxidonium by evaluating the following variables:

- (a) overall clinical improvement as assessed by investigators and subjects
- (b) mean duration of primary treatment of disease
- (c) mean number of days with fever $>38^{\circ}\text{C}$ and (or) disease symptoms
- (d) change in total and differential white blood cells (WBC) count (blood and urine) from baseline to the end of treatment (if data are available).

9. RESEARCH METHODS

9.1. Study design

This PASS is a local, multicentre, prospective, open-label, non-interventional, uncontrolled study.

Patients for whom Polyoxidonium is prescribed as a part of routine clinical practice will be eligible for this study. The decision to prescribe Polyoxidonium will be independent of the decision to enroll the subject into the study.

Primary treatment of a disease, Polyoxidonium administration, diagnostic procedures and assessments as well as visits schedule will be left at the discretion of investigators, according to local guidelines and routine clinical practices.

The study is explorative in nature. It is undertaken to systematically collect safety information in a community-based sample of subjects receiving Polyoxidonium therapy in routine care setting, to quantify potential risks, investigate potential risk factors and effect modifiers, or to provide evidence about the absence of risks.

9.2. Setting

The study will be conducted by physicians in primary or secondary health care setting. These may be immunologists or allergologists. These specialists usually prescribe Polyoxidonium in Slovakia. Health care centres will be considered as investigative sites.

In order to ensure that data represent the source population, potential investigators will be randomly selected from the available list of Slovakian immunologists and allergologists and will be invited to participate in this study. Every assented physician will be evaluated for his (her) expertise in the care of patients with secondary immunodeficiency, the ability to appropriately perform the study and overall interest in participation. It is expected that the study will be conducted at 15 investigative sites.

The decision to prescribe Polyoxidonium will precede and will be independent of the decision to enrol the patient into the study. Upon prescription of Polyoxidonium, investigator will offer each eligible patient an option to take part in the study, will inform about study procedures, give the informed consent form to read and answer all patient's questions. If this patient does not meet inclusion criteria or meets exclusion criteria or declines to participate, the investigator will pursue with the next patient. Since inclusion and exclusion criteria are very limited, it is expected that enrolled subjects will represent the source population (i.e., target patients of Polyoxidonium therapy) in Slovakia. To document the number of patients invited and assess selection bias in subject recruitment, screening logs will be used.

9.2.1. Subject inclusion criteria

To be eligible for participation in this study, the patient must:

- (a) be male or female at least 18 years of age.
- (b) receive Polyoxidonium prescription in accordance to the SmPC currently approved in Slovakia, i.e., for the treatment of any of the following diseases or conditions accompanied by secondary immunodeficiency:
 - chronic recurrent bacterial infection;
 - chronic recurrent viral infection;
 - acute bacterial infection;
 - acute viral infection;
 - allergic disease (pollinosis, bronchial asthma, atopic dermatitis).
- (c) be informed about the study and provide written consent to participate.

9.2.2. Subject exclusion criteria

The patient can't take part in the study if:

- (a) Polyoxidonium is contraindicated as per SmPC:
 - if there is known hypersensitivity to azoximer bromide or any of the excipients of Polyoxidonium;
 - if a woman is pregnant or breast-feeding;
 - if a woman of childbearing potential doesn't use effective contraception method (acceptable methods of birth control are: intrauterine device (IUD), diaphragm

with spermicide, contraceptive sponge, condom, vasectomy, hormonal contraceptive).

- (b) investigator deems necessary to prescribe more than 10 injections of Polyoxidonium per a single treatment course for the given patient.
- (c) patient has any clinically significant underlying medical illness, condition or disorder that, in the judgment of the investigator, could interfere with the conduct of the study.
- (d) patient is currently enrolled in any other investigational study or has participated in a interventional study within 4 weeks before enrolment.

9.2.3. Subject withdrawal criteria

Subject participation in the study must be prematurely discontinued for any of the following reasons:

- subject withdraws his/her consent;
- subject stops the treatment with Polyoxidonium;
- occurrence of AE or intercurrent condition that require discontinuation of treatment with Polyoxidonium;
- subject is lost to follow-up.
- subject has a confirmed positive serum or urine pregnancy test. Subjects with positive pregnancy tests will be followed to resolution (either miscarriage or normal birth, with or without complications). Refer to Section 11.5.

The reasons for study discontinuation must be recorded in a subject's medical records and eCRF.

A subject that discontinues from the study will not be replaced.

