9.2.4. Study visits

It is planned to observe each subject for one cycle of treatment with Polyoxidonium. In accordance with the Summary of Product Characteristics (SmPC), the treatment course consists of 5-10 injections depending on the disease. Thus, study duration for individual subject will take 7-23 days. There will be 5-10 study visits coinciding with routine visits to receive Polyoxidonium injections at the health care centre (see Study flow chart in Table 1). If any visit (scheduled or unscheduled) occurs within 30 days after the last injection of Polyoxidonium as a part of routine practice, information on adverse events will be recorded.

Table 1. Study flow chart

Study procedures	Study visits			
	First injection	Interim visits (3 to 8, depending on indication)	Last injection	Follow-up*
Day	Day 1		Day 7 to 23	
Inclusion/exclusion criteria	X			
Informed consent	X			
Demographic data	X			
Height and weight	X			
Medical history	X			
Physical examination**	X	X	X	
Information about relevant infection, allergic condition, etc.	X	X	X	
Vital signs (blood pressure, heart rate, body temperature)**	X	X	X	
Laboratory tests**	X	X	X	
ECG**	X	X	X	
Other diagnostic procedures**	X	X	X	
Polyoxidonium administration	X	X	X	
Concomitant medications	X	X	X	
Adverse events	X	X	X	X
Investigator's and subject's assessment of tolerability and improvement			X	

*any visit (scheduled or unscheduled) which occurs within 30 days after the last injection of Polyoxidonium as a part of routine clinical practice

**if undertaken as a part of routine clinical practice. Results of laboratory tests, ECG examinations and other diagnostic procedures should be recorded only if performed within 3 days before subject's enrolment and (or) during the study period.

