9.10. Other aspects

9.10.1. End of the study

The end of study is the date of the last visit of the last subject undergoing the study.

Early study termination decided by the Sponsor

The Sponsor reserves the right to prematurely stop or to interrupt the study at any time and for any reason; the decision will be communicated in writing to the investigator.

Early study termination decided by the RA/EC

The RA/EC may suspend or prohibit a study if it considers that the conditions of authorisation are not being met or has doubt about the safety or scientific validity of the study.

Early study termination decided by the investigator

The investigator must notify (30 days' prior notice) the Sponsor of his/her decision and give the reason in writing.

In all cases (decided by the Sponsor or by the investigator), the appropriate Regulatory Authorities and Ethics Committees should be informed.

Termination of the study in an individual case

Every subject has a right at any time and without indicating any reasons to withdraw his/her consent for further participation in the clinical study. Other possible reasons of subjects withdrawal from the study and procedures for discontinuation are described in Section 9.2.3.

10. PROTECTION OF HUMAN SUBJECTS**10.1. Ethical principles**

This study will be conducted in accordance with principles stated in the Declaration of Helsinki and subsequent amendments and in accordance with Guideline on Good Pharmacovigilance Practices (GVP) Module VIII-Post-authorisation safety studies [1], Good Pharmacoepidemiology Guidelines (GPP) [2] and Guide on Methodological Standards in Pharmacoepidemiology from The European Network of Centers for Pharmacoepidemiology and Pharmacovigilance (ENCePP) [3].

Before initiating the study, this study protocol will be submitted to the Slovakia State Institute for Drug Control and relevant ethics committees.

The study will start only after obtaining written approvals from the corresponding institutions.

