11.2 Recording of adverse events

During the study subjects must be carefully monitored for adverse events or special situations and the investigator will be responsible for the determination and documentation of them. Adverse events should be assessed in terms of their seriousness, severity and relationship to Polyoxidonium.

Adverse events will be determined in one of the three ways:

- observed by the investigator;
- identified by general questions about any changes in subjects well-being, asked at all study visits;
- spontaneously reported by the subjects to the investigator.

The investigator is responsible for ensuring that all AEs, irrespective of its severity, intensity, and suspected relationship to Polyoxidonium, are recorded in the subject's medical record and on the eCRF.

For each AE recorded on the eCRF, the investigator will make an assessment of seriousness (see Section 11.1.3 for seriousness criteria), severity (see Section 11.2.1), and causality (see Section 11.2.2). All measures, taken to treat adverse event, must be described in medical documentation.

After informed consent has been obtained, all adverse events, regardless of relationship to Polyoxidonium, will be reported until study closure. Any AE that is still ongoing at the completion/discontinuation visit will have an outcome of „ongoing“ in the eCRF, whereas the investigator will continue to follow up ongoing AEs and record information in the subjects medical documents. SAEs will be followed until the event resolves or the event or sequelae stabilise and this information will be reported to the Sponsor.

The investigator does not need to actively monitor subjects for adverse events once the study has ended. However, if becoming aware of any serious adverse events occurring to a subject within 30 calendar days after subject completed or withdrew the study, the investigator should report those to the Sponsor.

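### Adverse-event and renal data after the last injection are captured unevenly and incompletely: the reporting windows conflict, and the follow-up schedule collects adverse events only

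*Protocol*

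**What the plan says.** **Leaving the study.** Section 9.2.3 opens its list of withdrawal criteria with "Subject participation in the study must be prematurely discontinued for any of the following reasons". Two of the reasons are "subject stops the treatment with Polyoxidonium" and "occurrence of AE or intercurrent condition that require discontinuation of treatment with Polyoxidonium". Section 9.7.2 nevertheless keeps everyone who had at least one dose in the safety analysis, and Section 9.3.2 defines the main safety variables as proportions of subjects.

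**Length of observation.** Section 9.2.4: "Thus, study duration for individual subject will take 7-23 days". For a visit after treatment, planned or not, that "occurs within 30 days after the last injection of Polyoxidonium as a part of routine practice, information on adverse events will be recorded".

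**Other reporting rules.** Section 11.2: "After informed consent has been obtained, all adverse events, regardless of relationship to Polyoxidonium, will be reported until study closure". The same section says "The investigator does not need to actively monitor subjects for adverse events once the study has ended", and then asks for serious events that the investigator learns of in the 30 days after a subject completes or withdraws. Section 11.3 repeats that rule for serious events. Section 9.10.1: "The end of study is the date of the last visit of the last subject undergoing the study".

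**What is collected at follow-up.** In Table 1 the Follow-up column is marked for adverse events only. Laboratory, ECG and other diagnostic results are limited, in the Table 1 footnote and again in Section 9.3, to the 3 days before enrolment and the study period. Section 9.3 ties concomitant medication to the subject's participation.

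**The concern.** Both primary objectives are reported as frequencies or crude proportions of subjects. Such a figure can be interpreted only if every subject in the denominator is observed over a stated and comparable window. Here the window depends on which section a site follows, and the protocol does not say what happens to a subject who stops early.

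The data left out at follow-up matter for the event of interest. Section 9.3.1 describes renal toxicity mainly through creatinine, potassium, urea nitrogen, urine protein and ECG changes. Section 11.2.2 asks investigators to weigh recovery after stopping the drug, which can be seen only after the last injection. Section 9.7.1 stratifies the renal event by concomitant nephrotoxic medicines. None of these inputs has a mark in the Follow-up column.

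**Working it through.** **1. The plan's own figure, 7 to 23 days.** I built injection calendars from Section 9.2.6 with the first injection on Day 1.
- Acute, 5 injections: Day 7. Allergic, 5: Day 8. Acute, 10: Day 17. Every other day, 10: Day 19.
- Chronic (five every other day, then five twice weekly): Day 26 or 27 with alternating 3- and 4-day gaps, and Day 24 with 3-day gaps throughout.

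The lower bound reproduces. The upper bound does not under even spacing, although an irregular two-per-week pattern can reach Day 23. Sections 9.2.4 and 9.2.6 should be reconciled; I take no view on which is right. The steps below use the stated Day 7 and Day 23.

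**2. Observation time under each rule.**

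| Rule | Stops after injection 1 | Completer, Day 7 | Completer, Day 23 |
|---|---|---|---|
| Ends at last injection | 1 day | 7 | 23 |
| Last injection + 30 days (Section 9.2.4, if a routine visit occurs) | 31 | 37 | 53 |

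Until study closure, read as the last subject's last visit: the abstract plans first enrolment in May 2016 and the last visit in November 2016. From 31 May to 1 November is 155 days, and from 1 May to 30 November is 214 days, counting both ends. The last subject has only the treatment course.

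**3. Do the rules fit together?**
- If closure means the end of the whole study, Section 11.2 requires all adverse events for months, well past the 30 days of Section 9.2.4, and for a length set by enrolment date.
- If closure means the subject's own end, reporting of non-serious events stops at the last injection. Table 1 and Section 9.2.4 say it continues when a routine visit occurs.

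Neither reading agrees with Section 9.2.4.

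**4. How much of the window is at stake.** The share of the Section 9.2.4 window after the last injection is 30/(e + 30), where e is the day of the last injection: 30/37 = 81% for Day 7 and 30/53 = 57% for Day 23.

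**5. Illustration on assumed inputs.** Assume a constant hazard, a true risk p of a non-serious event over the whole window, 500 subjects who all have the same e, and a fraction v of the 30 days covered by routine contact. The observed fraction is f = (e + 30v)/(e + 30), and the chance of seeing at least one event is 1 − (1 − p·f)^500. I took p at the lower limits of common and uncommon in Section 9.5.

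| p | v = 1 | v = 0.5 (Day 7 / Day 23) | v = 0 (Day 7 / Day 23) |
|---|---|---|---|
| 1/100 | 99% | 95% / 97% | 61% / 89% |
| 1/1000 | 39% | 26% / 30% | 9% / 20% |

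**6. Effect of one common window.** The longest-to-shortest ratio among completers falls from 23/7 = 3.3 to 53/37 = 1.4. Against a subject who stops after one injection, it falls from 23/1 = 23 to 53/31 = 1.7.

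**The case against.** The strongest reply is that the protocol protects more than the withdrawal list suggests, and most of that reply stands.

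- The 30-day rule in Section 9.2.4 is anchored to the last injection, not to completion, so on its face it can cover a subject who stops early. Study visits are injection visits, so once injections stop there are no scheduled visits left to lose. Completers also end scheduled observation at their last injection.
- An event that leads to stopping happens while the subject is still in the study. It is recordable as an adverse event and as the reason for discontinuation, and the subject stays in the safety set. Serious events are followed until they resolve or stabilise.
- Section 11.1.1 counts an abnormal laboratory finding as an adverse event, and Section 9.3.1 encourages a work-up and requires adjudication when a renal effect is suspected.
- Section 9.10.1 defines the end of the study, not study closure. The sentence after the closure rule in Section 11.2 speaks of a completion or discontinuation visit, which favours the per-subject reading.

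A reader might therefore infer too much in three ways. First, that three windows are mutually incompatible: the 30-day routine-visit rule and the 30-day rule for serious events differ in scope and starting point but can coexist, and the conflict lies between study closure and Section 9.2.4. Second, that a creatinine rise after the last injection cannot be recorded: it can be, as an adverse event. Third, that harm in subjects who stop is lost, or that a given share of renal events goes missing: the event that prompts stopping is captured, and the documents give no discontinuation rate or risk from which to compute a share.

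The reply does not remove the two conflicting readings of study closure, the silence on follow-up of withdrawn subjects, or the missing follow-up marks for routine results and medicines.

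**Conclusion.** The point holds in limited form. Capture after the last injection is uneven and incomplete. The gap concerns late non-serious events, routine or symptom-free laboratory changes, values showing recovery after stopping, and concomitant nephrotoxic medicines not attached to an adverse event. In addition, a non-serious event unresolved at exit stays ongoing in the eCRF, with later information kept only in the medical documents.

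The firm figures are the window lengths: 57% to 81% of the Section 9.2.4 window lies after the last injection, and the study-wide reading of closure stretches reporting to about 155 to 214 days for a May 2016 subject. These rest on the stated Day 7 to Day 23 range and the planned dates. The detection probabilities rest on an assumed constant hazard and assumed coverage. They show sensitivity and do not estimate loss.

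This is a real contradiction with a cheap correction, worth making before enrolment because data not recorded may not be recoverable at analysis. It does not by itself undermine the study.

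**What to change.** - Reconcile Sections 9.2.3, 9.2.4, 9.10.1, 11.2 and 11.3 into one analysis window for every dosed subject: from first injection to 30 days after the last injection actually received, covering all adverse events, serious or not. Replace or define the term study closure accordingly.
- State that stopping treatment does not end data collection in that window; only withdrawal of consent or loss to follow-up does.
- In the Follow-up column of Table 1, mark laboratory tests, ECG, other diagnostic procedures and concomitant medication when done or recorded in routine care. Align the study-period limit in the Table 1 footnote and in Section 9.3.
- Report how many subjects had any contact within the window, split by completed and stopped early. Ascertainment will still depend on routine visits, and the reader needs to see how far it reached.

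The cost is protocol wording, existing eCRF pages opened at follow-up, and slightly more data entry from routine records. No visit or test is added, so the study stays non-interventional. The timetable can hold it: a last injection on 30 November 2016 plus 30 days is 30 December 2016, within the December 2016 end of data collection in Section 6.
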